Methodology	
The study will comprise 3 periods; 1) screening, 2) treatment, and 3) follow up.
 
During screening, informed consent will be obtained and evaluations of the participant's eligibility will be performed. At the beginning of the treatment period, participants will be randomised up to 28 weeks gestation (+ 6 days) in a 1:1 ratio, stratified by BMI and previous GDM to receive either metformin or matching placebo, in addition to usual care. The treatment period will be until delivery. Participants will be followed up at 4 weeks post-partum (+/- 7 days) by telephone, and 12 weeks postpartum (+/- 4 weeks) in the clinic for maternal and neonatal outcomes.

Statistical methods	
The primary analysis will be a comparison of the incidence of the composite primary outcome of proportion of participants needing insulin or fasting blood glucose ≥ 5.1 mmol/l at gestational weeks 32 or 38 between treatment and control arms, using an exact test for a binomial response. A secondary analysis will involve a comparison of the time to insulin initiation between the treatment groups, using the log-rank test and the proportional hazards model.

Health Economic Analysis	
The health economic analysis will consist of trial-based economic evaluation and will incorporate both cost effectiveness analysis and cost utility analysis to compare the alternative treatment strategies: 1) metformin in addition to usual care for GDM and 2) usual care for GDM.

313

314

315

316 **5. ABBREVIATIONS**

317

318	ACOG	American Congress of Obstetrics and Gynaecologists
319	ADA	American Diabetes Association
320	AE	Adverse event
321	ALT	Alanine Aminotransferase
322	ANOVA	Analysis of Variance
323	APH	Antepartum haemorrhage
324	AR	Adverse reaction
325	AST	Aspartate Aminotransferase
326	b.i.d.	Twice daily
327	BCSH	British Committee for Standards in Haematology
328	BMI	Body mass index
329	CDMS	Clinical data management system
330	CI	Confidence interval
331	CRF	Case report form
332	CRFG	Clinical Research Facility Galway

333	CT	Clinical trial
334	CTA	Clinical trial authorisation
335	DNS	Diabetes Nurse Specialist
336	DMF	Data management file
337	DOB	Date of birth
338	DTSQ	Diabetes Treatment Satisfaction Questionnaire
339	DSMB	Data safety and monitoring board
340	DSUR	Development safety update report
341	EBCOG	European Board and College of Obstetrics and Gynaecology
342	e-CRF	Electronic case report form
343	EDC	Electronic data capture
344	EDTA	Ethylenediaminetetraacetic acid

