1779 number of strategies to enhance follow-up for this outcome (e.g. home monitoring of weight).
1780

1781 11.3. Analysis Sets

1782 11.3.1. Intention-to-Treat Analysis Set

1783 The intention-to-treat analysis set, also termed full analysis set in the International Conference on
1784 Harmonization (ICH) E9 guideline, will include all randomized participants.
1785

1786 11.3.2. Safety Analysis Set

1787 The safety analysis set will include all randomized participants who received at least one dose of
1788 study medication.
1789

1790 11.4. Demographic and baseline disease characteristics

1791 Demographic and baseline characteristics of the study population will be summarized using graphical
1792 displays and descriptive statistics for each treatment group.
1793

1794

1800 **11.5. Effectiveness Analysis**

1801

1802 Suitable numerical and graphical techniques will be used to compare the primary and secondary

1803 responses and the balance in explanatory variables at baseline. The primary analysis will be a two-

1804 sample comparison of reduction in the proportion of participants needing insulin between treatment

1805 and control arms using an exact test for a binomial response.

1806

1807 We will also conduct a logistic regression analysis, to adjust for differences of baseline co-variates

1808 between treatment groups. Several strategies for including explanatory variables will be employed

1809 where penalisation for multicollinearity will be achieved using ridge penalties. Following this the most

1810 parsimonious subset of predictor variables will be identified using computationally intensive data

1811 driven techniques such as the classification trees and the Lasso penalty.

1812

1813 A secondary exploratory analysis will involve a comparison of the time to insulin initiation between the

1814 treatment groups, initially using the log-rank test and then the proportional hazards model in order to

1815 adjust for patient characteristics as appropriate. Repeated measures ANOVA will be used to evaluate

1816 the effect of intervention on secondary outcome of mean change in weight (from baseline to post-

1817 partum follow-up).

1818

1819 **11.5.1. Primary Effectivness Outcomes**

1820

1821 The primary efficacy outcome is a composite of:

1822

- Insulin initiation (Yes/No)
- Fasting glucose value <5.1 mmol/l and ≥ 5.1 mmol/l

1823

1824 **11.5.2. Secondary Effectiveness Outcomes**

1825

1826 Secondary efficacy outcomes include:

1827

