6.3 Randomisation and Blinding

Participants will be randomly assigned to receive either metformin or placebo in a 1:1 ratio. Random permuted blocks will be used to ensure similar numbers of participants in each intervention arm throughout the trial and equal numbers in each arm by the end of the study. A minimisation strategy will be used; allowing equal numbers of women with a BMI $\leq/ > 30$ and a history of GDM to be distributed between groups.

A web-based randomisation system will allow participating sites to login and obtain allocated treatment numbers and participant IDs after confirming eligibility through inclusion and exclusion criteria. The treatment number will correspond to a treatment kit at the site. This centralised system will ensure allocation concealment; preventing trial staff from knowing which treatment group will be allocated. Blocks of varying length will also be used to reduce the predictability of the allocation sequence

This trial will be conducted in a double-blind fashion with a placebo control identical to metformin tablets to avoid bias in assessing outcomes. Site Investigators, site personnel, participants, and outcome assessors will be blinded to treatment allocation.

In the case of an emergency, when knowledge of the participants's study treatment assignment is essential for the clinical management of the participant, an investigator may un-blind a participant. Any intentional or unintentional breaking of the blind will be recorded and reported to the sponsor as soon as possible.

7 Sample Size

Our sample size for testing this hypothesis is based on the following; a) 35% of women will require insulin in the control arm, based on information from the MiG trial and data from University Hospital Galway and University Hospital Cork; b) ability to detect a minimum of 33% relative risk reduction in the proportion of women requiring insulin in the experimental (metformin) group (40% to 28% absolute reduction; in the MiG trial only 40% of women on metformin required insulin); c) significance level of 0.05 and 80% power; d) drop-out rate of 5% or less; and e) non-adherence rate of 8% in metformin group. Based on these assumptions, we require a total of 550 participants. This sample size will also have 80% power to demonstrate a difference between the proportions of 12% or more (i.e. a reduction from 60-48%) in the secondary outcome of excessive GWG.

EMERGE NUIG-2016-01, Statistical Analysis Plan Version 1, 21/03/2023

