13.1 Primary Efficacy Analysis

The primary efficacy outcome is a composite of:

- Insulin initiation (Yes/No) or
- Fasting hyperglycemia ≥ 5.1 mmol/l at week 32 or 38.

Suitable numerical and graphical techniques will be used to compare the primary and secondary responses and the balance in explanatory variables at baseline. The primary analysis will be a two-sample comparison of reduction in the proportion of women needing insulin between treatment and control arms. A logistic regression model will be used to adjust for the stratifying variables, BMI and past history of GDM, along with other patient characteristics as appropriate.

A small number of participants (24) were randomised in more than one occasion for this study, each corresponding to a new pregnancy (49 in total). Note that the primary analysis described above will treat these duplicated pregnancies as independent. Although it is not expected that this issue will be influential in the overall conclusions derived from the analysis of the primary outcome, a sensitivity analysis will be performed considering only the first pregnancy per woman, among the 24 women who entered the study more than once.

A secondary exploratory analysis will involve a comparison of the time to insulin initiation between the treatment groups, initially using the log-rank test and then the proportional hazards model in order to adjust for patient characteristics as appropriate. Longitudinal data analyses based on linear mixed models will be used to evaluate the effect of intervention on secondary outcome of mean change in weight (from baseline to postpartum follow-up).

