13.2 Secondary Efficacy Analyses

Secondary efficacy outcomes include:

- Maternal morbidity at delivery (hypertensive disorders, antepartum and postpartum haemorrhage)
- Mode and time of delivery
- Maternal post-partum BMI, waist circumference, maternal gestational weight gain (GWG) blood glucose status, insulin resistance status and metabolic syndrome postpartum
- Proportion of maternal morbidities
- Infant birth weight
- Infant size (large/small/appropriate for gestational age)
- Neonatal height and head circumference at delivery
- Neonatal morbidities (Need for neonatal care unit, respiratory distress, jaundice, congenital anomalies, Apgar score)
- Neonatal hypoglycaemia (defined as plasma glucose <2.6mmol/L on one or more occasions starting 30-60 minutes after birth)

EMERGE NUIG-2016-01, Statistical Analysis Plan Version 1, 21/03/2023

- Proportion of infants with morbidities
- Treatment acceptability (Diabetes Treatment Satisfaction Questionnaire DTSQ and Rowan questionnaires)
- Quality of Life determined by EQ5D-5L questionnaire

Exploratory analyses based on generalised linear models will be used to estimate the treatment effect for each of the secondary outcomes while adjusting for the stratification variables and relevant baseline characteristics.

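### Time to insulin: the log-rank test is unstratified and the Cox model is not committed to BMI and past GDM, which costs power to the extent that these factors predict insulin need

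*SAP*

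**What the plan says.** Whether metformin delays insulin is the first secondary objective (SAP 5.1.2), and time to insulin is part of the first listed secondary endpoint (SAP 5.2.2). SAP 13.1 introduces the analysis as follows: "A secondary exploratory analysis will involve a comparison of the time to insulin initiation between the treatment groups". It is to be done "initially using the log-rank test and then the proportional hazards model in order to adjust for patient characteristics as appropriate". Protocol 11.5 (Effectiveness Analysis) has the same plan. Neither document names strata for the log-rank test or lists the Cox covariates, and neither states power or an event count for this comparison.

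On allocation, SAP 6.3 says "Participants will be randomly assigned to receive either metformin or placebo in a 1:1 ratio", and then "A minimisation strategy will be used; allowing equal numbers of women with a BMI" at or below versus above 30, and with a history of GDM, to be spread across the arms. The protocol synopsis describes allocation as "stratified by BMI and previous GDM to receive either metformin or matching placebo".

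Elsewhere the SAP carries these two factors into the analysis:
- Primary outcome (SAP 13.1): "A logistic regression model will be used to adjust for the stratifying variables, BMI and past history of GDM", with further characteristics where appropriate.
- Secondary outcomes (SAP 13.2): generalised linear models that estimate the treatment effect "while adjusting for the stratification variables and relevant baseline characteristics". Time to insulin is not in the list that this rule covers.

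**The concern.** When allocation balances a factor that predicts the outcome, the arms differ less by chance than under simple randomisation. An unstratified log-rank test does not know this. Its variance still includes the between-stratum variation that the design removed, so the standard error is too large and the true type I error falls below 5%. A test that compares the arms within strata matches the design.

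The Cox model that follows could repair this, but the SAP leaves its covariates open. The hazard ratio for the first secondary objective could therefore come from a model with or without the two allocation factors, while the SAP's other comparative models include them. What is at stake is some power, and a covariate choice left open until the data are seen.

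**Working it through.** **Inputs from the documents.** 1:1 allocation; alpha 0.05; 80% power for the binary insulin outcome; reduction from 40% to 28%; drop-out 5%; original N 550 (SAP 7); revised N 535 (SAP 8.1).

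**Assumptions not in the documents.** Two-sided test; proportional hazards; equal follow-up; 45% with BMI >30; 25% with past GDM; the two factors independent; biased-coin probability 0.8 for minimisation; hazard ratio of each factor for insulin need varied from 1 to 3.

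**Step 1: the plan's own figure.** Comparing 0.40 with 0.28, two-sided 5%, 80% power, with continuity correction (suited to the exact test in the protocol), gives 260 per arm. Then 260/0.95 = 274 per arm, 548 in total, against 550 stated. This matches only if the 8% non-adherence is not applied as a dilution of the effect.

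**Step 2: the same effect on the time scale.** HR = ln(1 − 0.28)/ln(1 − 0.40) = ln 0.72/ln 0.60 = 0.643. Schoenfeld events for 80% power: 4(1.96 + 0.842)²/(ln 0.643)² = 162. Expected events at N = 535 with 5% drop-out: 535 × (0.40 + 0.28)/2 × 0.95 = 173. Power = Φ(√173 × |ln 0.643|/2 − 1.96) = 82.7%.

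**Step 3: the tests compared.** The unstratified log-rank uses U = Σ(d₁ − n₁d/n) and V = Σ n₁n₀d(n − d)/[n²(n − 1)], summed over event times with all women pooled. The stratified test forms the same sums within the four BMI-by-past-GDM strata and then adds them. The third test is the Cox Wald test with both factors as covariates. Each scenario had 16,000 simulated trials, N = 535, allocation by minimisation, and the baseline hazard recalibrated so that the control insulin rate stayed at 40%. With treatment HR 0.643 this gives 178 to 181 events, slightly above 173 because women who drop out contribute events before they leave.

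| HR of each factor | Type I error, unstratified | Type I error, stratified | Power, unstratified | Power, stratified | Power, Cox with both factors |
|---|---|---|---|---|---|
| 1 | 4.9% | 4.9% | 83.5% | 83.4% | 83.5% |
| 1.5 | 4.7% | 4.9% | 82.2% | 82.9% | 83.0% |
| 2 | 3.9% | 4.9% | 81.7% | 84.2% | 84.3% |
| 3 | 2.9% | 5.0% | 77.1% | 84.3% | 84.3% |

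The unrounded gains from stratifying are −0.1, 0.8, 2.5 and 7.2 points. Simulation error is about 0.3 points on each power figure and up to 0.17 on type I error, so the type I shift at HR 1.5 is not clearly different from nothing. At 2 and 3 it is clear.

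**Step 4: does the allocation method matter?** The documents describe allocation as permuted blocks, as minimisation and as stratified. With stratified permuted blocks the gains are about 0, 0.8, 2.4 and 7.2 points. N = 550 shows the same pattern. The conclusion does not depend on which description is right.

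**The case against.** **The Cox model already covers this.** In the logistic sentence of SAP 13.1 the word 'other' implies that BMI and past GDM count as patient characteristics, so the Cox wording can be read to include them. The table shows that such a model matches the stratified test. This stands as far as it goes: the gap is a missing commitment. But the wording permits the factors without requiring them, and it does nothing for the log-rank test.

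**The plan has the same two steps for the primary outcome.** A plain two-sample comparison is followed by an adjusted model there too. True, but that adjusted model names the factors and this one does not.

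**The analysis is exploratory.** It carries no power claim, no rule makes its p-value decisive, and any error lowers type I error. This stands and limits the importance of the point. A reader might infer that the first secondary objective is decided by the log-rank p-value; the documents do not say so.

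**The size is unknown.** This also stands. The SAP preface names obesity and previous GDM as risk factors for GDM itself, not for needing insulin once GDM is diagnosed. Their use in allocation and in the primary model makes some prognostic value plausible, but gives no figure.

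**Larger gains can be produced.** With the baseline hazard fixed at 0.034 per week, treatment HR 0.68 and both factors at HR 3, a simulation of 508 women gives 78% power unstratified and 88% stratified. But the implied control insulin rate then climbs from about 41% (both factors at 1.5) to about 59%, against 35% or 40% in SAP 7. SAP 8.1 says the overall proportion on insulin was higher than planned but gives no value, so a 10-point gain is not supported.

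**The unadjusted hazard ratio is not wrong.** A reader might take an unadjusted hazard ratio nearer 1 as bias. It is a marginal effect, a different target from the within-stratum effect, so choosing the latter is partly a preference.

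**Conclusion.** The point holds as a conditional loss of efficiency and an inconsistency within the SAP. The log-rank test is unstratified and the Cox model is not committed to the two allocation factors, although the logistic model and the secondary generalised linear models adjust for them. If BMI and past GDM predict insulin need, the unstratified test is conservative. With about 180 events it loses about 0 points of power at a factor hazard ratio of 1, 0.8 at 1.5, 2.5 at 2 and 7 at 3. Those sizes rest on the assumed prevalences, proportional hazards, a 40% control rate and a treatment hazard ratio of 0.643.

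The documents do not support reading this as a threat to validity, or as a power loss certain to occur. There is no inflation of false positives, and with weak factors the loss is under one point. The case for change is that stratifying costs almost nothing in power (0.1 point, within simulation error, when the factors are not prognostic) and brings this analysis into line with the design and the rest of the SAP.

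**What to change.** In SAP 13.1, replace the description of the two tests with:

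> Log-rank test stratified by BMI (≤30/>30) and past GDM; the hazard ratio comes from a Cox model with the same two factors as strata or fixed covariates.

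Choose strata or covariates in the text, so that one model is fixed. Keep the unstratified log-rank test as a sensitivity analysis. State that the hazard ratio is a within-stratum (conditional) effect, as the odds ratio from the planned adjusted logistic model already is.

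Make the change before unblinding. SAP 8.2 plans an analysis with the randomisation codes before database lock, so the text should be settled before that analysis. The cost is one sentence in the SAP and one option in the code. Four strata with about 180 events bring no material loss of power, and no new data are needed. The one real consequence is the change of target from a marginal to a conditional hazard ratio.

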13.2 Secondary Efficacy Analyses

Secondary efficacy outcomes include:

- Maternal morbidity at delivery (hypertensive disorders, antepartum and postpartum haemorrhage)
- Mode and time of delivery
- Maternal post-partum BMI, waist circumference, maternal gestational weight gain (GWG) blood glucose status, insulin resistance status and metabolic syndrome postpartum
- Proportion of maternal morbidities
- Infant birth weight
- Infant size (large/small/appropriate for gestational age)
- Neonatal height and head circumference at delivery
- Neonatal morbidities (Need for neonatal care unit, respiratory distress, jaundice, congenital anomalies, Apgar score)
- Neonatal hypoglycaemia (defined as plasma glucose <2.6mmol/L on one or more occasions starting 30-60 minutes after birth)

EMERGE NUIG-2016-01, Statistical Analysis Plan Version 1, 21/03/2023

- Proportion of infants with morbidities
- Treatment acceptability (Diabetes Treatment Satisfaction Questionnaire DTSQ and Rowan questionnaires)
- Quality of Life determined by EQ5D-5L questionnaire

Exploratory analyses based on generalised linear models will be used to estimate the treatment effect for each of the secondary outcomes while adjusting for the stratification variables and relevant baseline characteristics.

13.3 Other Efficacy Analysis

Health economic outcomes include:

- EQ5D-5L
- Quality Adjusted Life Years (QALYs)
- Costs of healthcare associated with the intervention and control arms

The Health Economic and Policy Analysis (HEPA) research team at the University of Galway have previous experience in the design and conduct of economic evaluation alongside randomised controlled trials within an Irish healthcare context. The health economic analysis will consist of trial-based economic evaluation. It will incorporate both cost-effectiveness analysis and cost utility analysis to compare the alternative treatment strategies: (1) metformin in addition to usual care for GDM (that is, MNT and/or insulin); and (2) usual care for GDM. The economic evaluation will be undertaken consistent with the guidelines issued by Health Information and Quality Authority (HIQA) (2014) for the evaluation of technologies in Ireland. The basic tasks of the evaluation are to identify, measure, value and compare the costs and outcomes of the alternatives being considered. Evidence collected on resource use and clinical outcome measures alongside the trial will provide the basis for the analysis over the trial follow up period. A healthcare provider perspective will be adopted for costing. This will reflect the healthcare resources consumed in operating both treatment strategies including those relating to health professional time input, diagnostic testing, dietary, exercise and prescription medication interventions (metformin and insulin), consumables and materials, equipment and overheads. Healthcare resource use for both treatment arms will be recorded alongside the trial. Unit costs will be applied to value resource use data and calculate the various costs of care.

As detailed above, significant attention will be paid to collecting relevant data on health outcomes alongside the trial. For the cost effectiveness analysis, the treatment strategies will be compared based on the effectiveness data for the primary clinical outcome. For the cost utility analysis, effectiveness will be evaluated based on Quality Adjusted Life-Years (QALYs), which is the preferred outcome measure for economic evaluation as it allows for comparison of relative cost effectiveness both within and beyond the clinical area of interest (Drummond et al, 2015). In this case, patient responses to the EQ5D 5L questionnaire (Euroqol Group, 1990) at baseline and follow up will be used to compute QALYs for the two treatment arms. The health economic analysis will employ the standard approach for

comparing alternative treatment strategies in terms of costs and health outcomes. An incremental analysis will be undertaken to provide information on the marginal costs and effects of the metformin plus standard GDM care intervention relative to the standard GDM care alternative through calculating incremental cost-effectiveness ratios. The analysis will report the incremental cost effectiveness from a publicly funded health system perspective in line with HIQA guidance (HIQA, 2014). Univariate, multivariate and probabilistic sensitivity analyses will be employed to address uncertainty in the study. Budget impact analysis will be undertaken for metformin in addition to usual care for GDM strategy.

14 Safety Analyses

